ECOG	Eastern Cooperative Oncology Group
FDA	Food and Drug Administration
Fx	Fractions
GCP	Good Clinical Practice
HIPAA	Health Insurance Portability and Accountability Act
LRC	Local Regional Control
ICM	Insertable Cardiac Monitoring
IMRT	Intensity-Modulated Radiotherapy
IRB	Institutional Review Board
IV	Intravenous
MRI	Magnetic Resonance Imaging
OS	Overall Survival
PBS	Pencil Beam Scanning
pCR	Pathologic Complete Response
PFS	Progression Free Survival
PHI	Protected Health Information
PI	Principal Investigator
PRO	Patient Reported Outcomes
QOL	Quality of Life
RT	Radiotherapy
RTOG	Radiation Therapy Oncology Group
SAE	Serious Adverse Event/Serious Adverse Experience
SBRT	Stereotactic Body Radiation Therapy
SOC	Standard of Care
SCD	Sudden Cardiac Death
SOP	Standard Operating Procedure

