16.32 Definitions and Analyses of Secondary Endpoints

16.321 Analysis Plan

The analysis for this trial will commence when 24 patients have either died or reached the 12 month data point. Cardiac event as recorded in section 11.1 would be used for our analysis. We expect to see 3 or more cardiac events grade 3 or higher based on the CTC AE V5.0.

16.322 The following definitions are used for the secondary endpoints of interest:

All end points would be measured studied from the date of patient registration

- Acute adverse events: all AEs occurring within the first 6 months from the date of enrollment.
- Late adverse events: all AEs occurring after the first 6 months from the date of enrollment.
- Loco-regional recurrence: local recurrences of the cancer in the same location where the disease was found on any diagnostic or staging study.
- Distant recurrence: metastatic cancer that has either been biopsy confirmed or clinically diagnosed as recurrent.
- Disease- free survival: the time from study registration any local, regional, distant failure, or death.
- Cause specific survival: the time from registration to death due to cancer. If the cause of death is unknown or difficult to establish,

patients with a distant failure at the time of death would be censored as dying from cancer.

- Cardiac event free survival: the time from registration to cardiac event or death.
- Cardiac death: the time from registration to death due to cardiac reasons. Cardiac death would include documented congestive heart failure, myocardial infarction, arrhythmia*, heart block*, or any other cardiac cause documented in the medical records, death certificate, or autopsy as one of the major contributing causes of death.

*Any lethal electrophysiologic change documented by the ICD before death would also be included.

- Overall survival: the time from registration to death due to any cause.

16.323 Adverse events: All eligible patients that have initiated treatment will be considered evaluable for assessing adverse event rate(s). The maximum grade for each type of adverse event will be recorded for each patient, and frequency tables will be reviewed to determine patterns. Additionally, the relationship of the adverse event(s) to the study treatment will be taken into consideration.

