Analyses for secondary endpoints will be descriptive in nature. Adjustment for multiple comparisons for the secondary analyses will not be done due to the exploratory nature of this research. Statistical tests on endpoints (t-test for continuous data; Wilcoxon rank-sum test, Fisher's exact test, or Chi-square test for ordinal data) will be utilized to determine differences at any particular time point. Graphical displays will be produced, such as mean profile plots or bar charts. Descriptive statistics of frequency (percentage) will be used to summarize AE incidence and severity as measured by the CTCAE 5.0. 95% confidence intervals will be constructed around point estimates.

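### Section 16.322 defines loco-regional recurrence as local recurrence only, so a first relapse in a regional node uninvolved at staging is not counted, although disease-free survival treats regional failure as an event

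*Combined protocol and SAP*

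**What the plan says.** Three definitions in section 16.322 bear on this point.

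- The loco-regional endpoint is limited to "local recurrences of the cancer in the same location where the disease was found on any diagnostic or staging study".
- For disease-free survival, the plan takes "the time from study registration any local, regional, distant failure, or death".
- The distant endpoint is described as "metastatic cancer that has either been biopsy confirmed or clinically diagnosed as recurrent".

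The cause-specific survival definition in the same list also relies on the word distant. When the cause of death is unknown or hard to establish, the presence of a distant failure decides whether the death is classed as due to cancer.

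No other section defines regional failure. The abbreviation list contains "Local Regional Control", but that term is not used as an endpoint. On the role of these endpoints, section 16.32 states: "Analyses for secondary endpoints will be descriptive in nature".

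**The concern.** The label of the endpoint promises two components, local and regional, but the rule delivers one. It restricts the event twice: the recurrence must be local, and it must lie where disease was already documented. A regional node that was negative at staging fails both tests.

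The disease-free survival definition separates local, regional and distant failure and counts all three. Regional failure is thus a recognised event in this plan, yet no recurrence endpoint clearly receives it.

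What is at stake is the reported loco-regional recurrence proportion. Someone abstracting charts by the wording would leave such a patient out of it, or enter the patient as distant because a nodal deposit can be called metastatic. Someone abstracting by the label would include the patient. The same chart could be coded in different ways.

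**Working it through.** The plan states no figure that depends on this definition, so there is none to reproduce. The check is to apply the three definitions, as worded, to four kinds of first relapse.

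| First relapse | Loco-regional recurrence | Distant recurrence | Disease-free survival |
|---|---|---|---|
| Primary tumour bed | Counts | Does not count | Event (local) |
| Regional node involved at staging | Counts, if the node is taken as a place where disease was found | Not needed | Event |
| Regional node not involved at staging | Does not count | Not settled by the text | Event (regional) |
| Distant organ | Does not count | Counts | Event (distant) |

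Only the third row is a problem. There are two ways to code it, and one patient can follow only one of them:

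1. The relapse is entered in neither recurrence endpoint. The patient then has a disease-free survival event and no matching recurrence record.
2. The relapse is entered as distant because it is called metastatic. That conflicts with the disease-free survival definition, which keeps regional and distant apart, and the loco-regional count is still one too low.

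In both cases the patient is a disease-free survival event, so that endpoint does not change.

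One possible escape is to let the words about any diagnostic study include the later scan that shows the relapse. But the rule speaks of recurrence where disease was found, in the past tense. If the scan showing the relapse could itself qualify, the same-location condition would exclude nothing.

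**Size.** The documents give no rate of loco-regional failure and no share of failures arising in previously clear nodes. The following inputs are assumptions, chosen only to show the order of magnitude:

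- planned enrolment of 24 patients (sections 1.5 and 16.22);
- assumed loco-regional failure within the year, including new regional nodes: 20% to 30%;
- assumed share of those that first appear in a regional node not involved at staging: 10% to 30%.

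Patients left out = 24 × failure rate × share.

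- Low end: 24 × 0.20 × 0.10 = 0.48 patients, and 0.48 / 24 = 2%.
- High end: 24 × 0.30 × 0.30 = 2.16 patients, and 2.16 / 24 = 9%.

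In whole patients this is about zero to two. Each patient left out lowers the proportion by 1/24, or 4.2 percentage points.

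**The case against.** The strongest reply is that little depends on this line. The primary goal (section 2.1) is cardiac, and no exploratory goal (section 2.2) concerns recurrence. The endpoint carries no hypothesis, decision or stopping rule. All of that stands, and it sets the priority.

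A second reply is that the intention is obvious: a coder guided by the label and by the disease-free survival definition would file a new regional node as loco-regional. That may happen, so the loss is possible rather than certain. It does not rescue the definition, because that coder would be departing from its wording.

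A third reply is that coding rules may exist elsewhere. Section 1.5 mentions a registry under separate consent, and the treatment text in section 7.1 is redacted. Neither is shown to settle the point, but rules outside these documents cannot be excluded.

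A reader might also infer larger consequences, which the documents do not support:

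- **Loco-regional control would be overstated.** No such endpoint is planned; the term appears only among the abbreviations.
- **The disease-free survival components would fail to add up in the report.** The plan promises no breakdown of that endpoint by component.
- **Cause-specific survival would be distorted.** One patient would need an isolated new-node relapse, a coder who files it as distant, and a death of unclear cause. Starting from zero to two such relapses, this is remote.

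**Conclusion.** The definition is wrong as written, and the priority is low. Followed literally, it leaves a first relapse in a regional node uninvolved at staging out of the loco-regional count, while the same list treats regional failure as an event and gives distant recurrence no boundary. This conclusion rests on the wording alone and does not depend on any rate.

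The loco-regional recurrence proportion could be understated. By how much is unknown; zero to two of about 24 patients is plausible under the assumed rates. The range of 2 to 9 percentage points should not be read as an estimate of bias, because both inputs are assumptions and the low end is half a patient. It is possible that no enrolled patient is affected. The primary cardiac endpoint and disease-free survival do not change.

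**What to change.** Amend section 16.322 before recurrences are abstracted:

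1. Define loco-regional recurrence as recurrence at the primary site or in the regional lymph nodes for that primary, whether or not the node was involved at staging. Take the regional nodes from the staging system used at diagnosis, and name that system for each tumour type, since section 12.0 lists lung, esophageal and other thoracic cancers.
2. Define distant recurrence as metastatic disease outside those sites, and keep the present criterion of biopsy confirmation or clinical diagnosis.
3. Use the same terms in disease-free survival and in the cause-specific survival rule.

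Progression need not be added to the definition; the gap does not call for it.

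The cost is a few lines of wording and a matching instruction for abstractors. Treatment, visits and sample size are not affected. One practical limit remains: the test schedule in section 4.0 lists no tumour restaging imaging, so the site of failure has to come from the medical record. The abstraction form should allow for cases where the record does not identify the site.

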4.0 Test Schedule

- Implanted cardiac monitors would be placed prior to starting radiation treatments and monitored for 12 months after treatment (for a total of 14 months). Baseline recordings of the cardiac rhythm would be done prior to RT, 4 weeks post-RT, 3 months post-RT, 9 months post-RT, and 12 months post-RT.
- Blood bio-banking would be done as seen in Appendix 1: prior to RT, 4 weeks post-RT, 3 months post-RT, 9 months post-RT, and 12 months post-RT.
- Dried blood spot would be collected at home by the patient prior to RT, 4 weeks post-RT, 3 months post-RT, 9 months post-RT, and 12 months post-RT.
- All patients will complete SOC treatment as defined by his treating oncologists including evaluation by cardiology and cardiac MRI evaluations.
SOC procedures are highlighted in blue—they are considered standard for the care for this patient population and currently done in the Cardio-Oncology Clinic at Mayo Clinic in Arizona. All SOC procedures are recommended, but may be omitted at the discretion of the physician or patient.
- Cardiac MRI information may be shared with ASU for additional MRI post processing.
De-identified images or raw MRI data will be used.

Table 5.0		Post-Tx ⁵					
	PRE-TX (-120 to 0 days prior to Tx)	TX	4 weeks (+/- 2 WEEKS)	3 months (+/- 6 WEEKS)	9 months(+/- 6 WEEKS)	12 months (+/- 6 WEEKS)	Unscheduled
Procedures							
Informed Consent	X						
Cardiology evaluation	X						X ¹
Cardiac history	X						
12-lead ECG	X			X			X
Holter monitor, if clinically indicated	X						X
2 D transthoracic ECHO	X ⁷			X			X

Cardiac Labs (troponin, CK, CKMB, pro- BNP,BMP, CBC)	X		X	X	X	X	X
Implanted cardiac monitor ^{r6}	X ⁷						
Explant cardiac monitor ^{r6}							X
Cardiac recordings via implanted cardiac monitor ^{r6}	X ⁷		X	X	X	X	X
SOC RT Treatment ²		X					
ECOG	X						X
AE	X	X	X	X	X	X	X
Bio- banking(blood) ^r	X		X	X	X	X	
Dried blood spots (TGEN) ^r	X		X	X	X	X	
Cardiac MRI ^r	X ^{3, 7}			X ³		X ³	
Pulmonary Function Test	X ⁴					X	

¹ Additional cardiac follow-up visits as clinically indicated per standard of care treatment.

² Additional radiation oncology follow-up visits; scheduled per standard of care treatment.

³ Cardiac MRI as clinically indicated as per SOC cardiology evaluation; however study will pay for all patients as a research cost.

⁴ Pulmonary function tests obtained pre-treatment (within 6 months of the start of treatment)

⁵ Time is measured from the date radiation therapy is completed.

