13.0 Treatment/Follow-up Decision at Evaluation of Patient

- 13.1** A patient is deemed *ineligible* if after registration, it is determined that at the time of registration, the patient did not satisfy each and every eligibility criteria for study entry. The patient will go off study and continue in the monitoring phase.
- If the patient received MR and PET for radiotherapy planning, all data up until the point of confirmation of ineligibility must be submitted.
- 13.2** Those patients who will not receive any radiation treatment or who will receive radiation treatment elsewhere will go off study.

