16.0 Statistical Considerations and Methodology

16.1 Study Design

This is a single-arm, observational study designed to determine the 12-month cardiac event rate after radiation or chemo-radiation for thoracic malignancies meeting the eligibility criteria.

16.11 Primary Endpoint:

A cardiac event will be defined according to section 11.1 and occurring during the first 12 months after radiation or chemo-radiation. An evaluable patient will be classified as a failure (cardiac event) for the primary endpoint if the patient had any of the events listed in section 11.1 during the time period. All patients meeting the eligibility criteria who have signed a consent form, have begun RT, and have not experienced a major treatment violation within the first month of treatment will be evaluable for response.

16.2 Statistical Design:

This is an observational study intended to provide preliminary estimates of cardiac event rate in patients receiving radiation or chemo-radiation. Safety of the implanted cardiac monitoring device will be described. Point estimates and two-sided 95% confidence intervals will be computed. All patients meeting the eligibility criteria who have signed a consent form and have begun treatment will be included in the descriptive estimates.

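### Survival is timed from registration but, as the plan reads, described only in patients who started treatment, so overall and cause-specific survival are slightly overstated and cardiac death understated

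*Combined protocol and SAP*

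**What the plan says.** **Time origin.** Section 16.322 sets one origin for all secondary endpoints: "All end points would be measured studied from the date of patient registration". The individual definitions repeat it: "Overall survival: the time from registration to death due to any cause"; "Cause specific survival: the time from registration to death due to cancer"; "Disease- free survival: the time from study registration any local, regional, distant failure, or death". Cardiac event free survival and cardiac death use the same origin. Under section 6.1, registration needs consent, eligibility and logging in the tracking system. It does not need RT to have started.

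**Analysis set.** Section 16.2 states: "All patients meeting the eligibility criteria who have signed a consent form and have begun treatment will be included in the descriptive estimates". Section 16.32 then says "Analyses for secondary endpoints will be descriptive in nature", which brings the survival endpoints under that sentence. Section 13.2 adds: "Those patients who will not receive any radiation treatment or who will receive radiation treatment elsewhere will go off study". Section 11.4 replaces a patient who is removed before any study data are obtained.

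**The wait.** Section 4.0 places cardiac testing and monitor insertion between enrollment and RT. Table 5.0 lets the pre-treatment procedures, consent among them, fall up to 120 days before treatment. The plan specifies no delayed entry, landmark or RT-start clock.

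**The concern.** Inclusion depends on something that happens after the clock has started. A patient who dies between registration and treatment cannot enter the estimate, yet every patient who does enter carries an interval in which death was impossible by construction. This is immortal time.

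Overall and cause-specific survival are then too favourable, and cardiac death too rare, by an amount that depends on how long patients wait. Disease-free survival is also affected when progression during the wait cancels RT and so removes the patient. Early death after thoracic RT is the rationale of the study (section 1.3), and section 16.5 commits the secondary endpoints to public results reporting, so the figures should mean what their definitions say.

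**Working it through.** The plan states no survival figure to reproduce. The check below sizes the effect of the mismatch.

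**Inputs**
- 12-month mortality of about 20%, from section 16.22. The section gives no time origin for it. Under a constant hazard the results are the same whether it runs from registration or from RT start.
- Constant hazard: assumption.
- Wait w from registration to treatment start: not stated. I use 14, 30 and 60 days as assumptions, and 120 days as the outer limit from Table 5.0.
- N = 24, from section 16.22.

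**Formula.** Survival from registration is S(t) = 0.80^(t/365). Among patients who survive the wait, 12-month survival on the registration clock is S(365)/S(w) = 0.80^(1 − w/365). Since S(w) cannot exceed 1, this is never below S(365). The chance of dying in the wait is 1 − 0.80^(w/365).

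| Wait (days) | 1 − w/365 | 12-month survival shown | 12-month mortality shown | Overstatement (points) | Expected deaths in the wait per 24 registered |
|---|---|---|---|---|---|
| 14 | 0.962 | 80.7% | 19.3% | 0.7 | 0.2 |
| 30 | 0.918 | 81.5% | 18.5% | 1.5 | 0.4 |
| 60 | 0.836 | 83.0% | 17.0% | 3.0 | 0.9 |
| 120 | 0.671 | 86.1% | 13.9% | 6.1 | 1.7 |

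A simulation of 2 million patients at each of 14, 28, 60 and 120 days agrees. Treatment starters timed from registration show 80.7%, 81.4%, 83.0% and 86.1%. All registered patients timed from registration, and starters timed from RT start, both return 80.0%.

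**If the hazard before RT differs.** With a pre-RT hazard m times the later hazard h = −ln(0.80)/365 per day, the overstatement is exp(−h(365 − w)) × (1 − exp(−m·h·w)). For m from 0.5 to 2 it is 0.3 to 1.4 points at 14 days, 0.7 to 2.9 at 30, 1.5 to 5.9 at 60 and 3.1 to 11.8 at 120.

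**Against sampling error.** The count nearest to 80% of 24 is 19 survivors. The exact 95% interval for 19/24 (79.2%) is 57.8% to 92.9%.

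**By endpoint**
- Overall survival: the full shift in the table.
- Cause-specific survival and cardiac death: the same mechanism, acting only on pre-treatment deaths from that cause, so the shift is smaller than the all-cause figure.
- Disease-free survival: a failure in the wait that does not stop treatment still counts. Only deaths, and failures that prevent treatment, are lost.
- Cardiac event free survival: section 11.1 counts any cardiac event after registration, and the monitor is meant to be in place before RT. A patient with a non-fatal event who then starts treatment stays in the set and counts as a failure. Again, only deaths or events that prevent treatment are lost.

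**The case against.** **No sentence names an analysis set for the survival endpoints.** This is true. The 16.2 sentence sits beside text on the cardiac event rate and device safety. Section 16.323 restricts adverse events to treated patients, while the survival definitions above it carry no such limit. Section 16.3 promises summaries for all patients, 16.321 waits until 24 patients have died or reached 12 months, and section 4.1 lists death as its own end of study participation, so a pre-treatment death might well be recorded. The restriction is therefore an inference. It is still the natural one: the secondary analyses are called descriptive, 16.2 defines who enters the descriptive estimates, the all-patients sentence concerns summary statistics, and 13.2 takes untreated patients off study. If all registered patients were intended, 16.322 needs to say so and 13.2 needs to change.

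**Treatment in 16.2 may not mean RT.** Section 16.11 names RT, 16.2 does not, and section 3.16 allows systemic therapy or surgery before RT. If those count as treatment, the wait is shorter for the patients concerned. This stands, and it lowers the size.

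**The effect is small and the endpoints are secondary.** This also stands. The 14-month monitoring total in section 4.0 leaves only about two months for the monitored wait plus the RT course. No survival test or decision rule depends on these figures, and the primary endpoint does not use this clock.

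**Stronger readings that the documents do not support.** A reader might infer that every survival endpoint is biased by the full amount. Section 11.1 and the disease-free survival definition rule that out. A reader might also infer that a planned comparison with RTOG 0617 mortality is spoiled. Section 16.22 uses that 20% only to inflate the sample size, and no such comparison is planned.

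**Conclusion.** The concern holds as a small, systematic mismatch between time origin and analysis set. On the natural reading of 16.2, 16.32 and 13.2, the expected direction is certain for three endpoints: overall and cause-specific survival up, cardiac death down. Disease-free and cardiac event free survival are affected only in part.

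The likely overstatement of 12-month overall survival is about 0.7 to 1.5 points for a wait of 14 to 30 days and 3.0 points for 60 days. The 6.1 points at 120 days belong to the edge of a permitted window and should not be read as an expected value. All of these are small beside an interval of 57.8% to 92.9%. They rest on 20% 12-month mortality, a constant hazard and an assumed wait. If no registered patient dies while waiting, overall survival on the registration clock is unaffected by the exclusion.

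The point does not threaten the primary result. It merits correction because the bias runs one way and wording alone can remove it.

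**What to change.** In section 16.322, make the time origin and the analysis set agree, by one of two routes.

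(a) For patients who start RT, use the first RT fraction as time zero, or keep registration as time zero with delayed entry at the first fraction. Report deaths, failures and cardiac events between registration and RT start as separate counts. State in 16.2 that the qualifying event is the start of RT, so that it matches 16.11.

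(b) Keep registration as time zero, state that all registered eligible patients are included in the survival endpoints, and amend 13.2 so that patients who receive no RT stay in survival follow-up. Section 11.4 should be checked against this, because it ends data submission for patients removed before any study data exist.

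**Cost.** Route (a) is a few lines of text. No section lists the RT start date as a collected item, so confirm that the case report form holds it. Pre-RT cardiac events move out of cardiac event free survival into the separate count. Route (b) adds survival follow-up for the few patients who never start RT. Either way the reported survival figures can be expected to be slightly less favourable. Neither route needs a larger sample.

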
4.1 Event Monitoring/Survival Follow-up

Patients will be “on study” until one year after completion of RT, withdrawal of consent, lost to follow-up, study closure, or death.

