10.3 Other Required Reporting

10.31 Unanticipated Problems Involving Risks to Subjects or Others (UPIRTSOS)

Unanticipated Problems Involving Risks to Subjects or Others (UPIRTSOS) in general, include any incident, experience, or outcome that meets **all** of the following criteria:

1. Unexpected (in terms of nature, severity, or frequency) given (a) the research procedures that are described in the protocol-related

documents, such as the IRB-approved research protocol and informed consent document; and (b) the characteristics of the subject population being studied;

2. Related or possibly related to participation in the research (in this guidance document, possibly related means there is a reasonable possibility that the incident, experience, or outcome may have been caused by the procedures involved in the research); and
3. Suggests that the research places subjects or others at a greater risk of harm (including physical, psychological, economic, or social harm) than was previously known or recognized.

Some unanticipated problems involve social or economic harm instead of the physical or psychological harm associated with adverse events. In other cases, unanticipated problems place subjects or others at increased *risk* of harm, but no harm occurs.

Note 1: If there is no language in the protocol indicating that pregnancy is not considered an adverse experience for this trial, and if the consent form does not indicate that subjects should not get pregnant/impregnate others, then any pregnancy in a subject/patient or a male patient's partner (spontaneously reported) which occurs during the study or within.

Note 2: research procedures include: cardiac monitoring device placement and extraction, cardiac monitoring employing the cardiac monitoring device, cardiac MRI, dried blood collection, and blood biobanking. Cancer treatment is per SOC and at the discretion of the treating physicians and not part of the research procedures. Expected toxicities as part of the SOC cancer treatment will not be considered for IRB reporting.

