11.2 Safety Outcome Measures

In-office placement of the device with local anesthetic is very safe. Likewise, the device itself is very safe. Risks of this insertion are truly minimal but may include

bleeding or infection. We will monitor any adverse events related to the placement of the device.

- 11.3** This is an observational study designed to follow cardiac changes in patients with esophageal or lung cancer who receive curative SOC thoracic RT or CRT. Data regarding the adverse events per SOC, surgery, RT, chemotherapy, and regular standard of care follow-up will be observed and collected as part of the SOC.
- 11.4** A patient is deemed ineligible if he/she is removed from the study for any reason before any study data is obtained. On-study material and Cancel Notification/Termination Form must be completed in CRF. No further data submission is necessary. Subject will be replaced in accrual number.
- 11.5** If the subject participated in study, all data up until the point of confirmation of ineligibility must be submitted.

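### The reported device-safety rate leaves out patients who received the cardiac monitor but never began cancer treatment or were found ineligible

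*Combined protocol and SAP*

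**What the plan says.** **Aim.** Section 16.2 states: "Safety of the implanted cardiac monitoring device will be described". Point estimates with two-sided 95% confidence intervals are to be given.

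**Analysis set.** The same section continues: "All patients meeting the eligibility criteria who have signed a consent form and have begun treatment will be included in the descriptive estimates". Section 16.323 repeats the condition for adverse events (AEs): "All eligible patients that have initiated treatment will be considered evaluable for assessing adverse event rate(s". No separate set of implanted patients is defined anywhere.

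**Timing of the implant.** Section 4.0 has the monitor placed before RT starts, within a pre-treatment column that runs from 120 days before treatment. Footnote 7 to Table 5.0 allows it after the start of RT if scheduling prevents earlier placement.

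**Leaving the study.** Section 13.2: "Those patients who will not receive any radiation treatment or who will receive radiation treatment elsewhere will go off study". Otherwise, under section 4.1, a patient stays on study "until one year after completion of RT, withdrawal of consent, lost to follow-up, study closure, or death".

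**Device events.** Section 11.2: "We will monitor any adverse events related to the placement of the device". Note 2 to section 10.31 says that "research procedures include: cardiac monitoring device placement and extraction", and section 19.2 lists implant and explant as research-funded. Table 5.0 marks explant only in the Unscheduled column, where AEs are marked too.

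**The concern.** Cancer treatment here is standard of care, and the ICM is the implanted research device. A safety denominator should start from exposure to the thing whose safety is described. This one starts from a later and different event, the beginning of cancer treatment, and also requires eligibility. A patient can therefore have the device inserted, have a bleed or an infection at the site, not go on to treatment, and be absent from both numerator and denominator of the device rate.

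At stake is the credibility of a small descriptive safety statement. With about 24 patients, a single omitted complication is the difference between reporting none and reporting some. If a complication ever contributed to treatment not starting, the exclusion would favour the device. The documents neither show nor rule out that this would happen.

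**Working it through.** **Step 1. What happens to each kind of implanted patient under the written rules.**

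| Implanted patient | In the 16.2 and 16.323 sets? | Other rules that apply |
|---|---|---|
| Eligible, starts RT at the centre | Yes | Followed to one year after RT |
| Implanted after RT began (footnote 7) | Yes, if eligible | As above |
| Starts no cancer treatment | No | Off study (13.2) |
| Starts systemic therapy, never RT | Unclear: 16.323 says treatment, while 16.11 says RT | Off study (13.2) |
| RT given elsewhere | Unclear | Off study (13.2) |
| Found ineligible after registration | No | Data submitted up to confirmation (11.5); off study but continues in a monitoring phase (13.1) |

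The third and last rows are plain exclusions from the device rate. The two unclear rows show that the sets were not written with device exposure in mind. Section 13.1 mentions continued monitoring for ineligible patients; section 13.2 has no such provision for patients without RT.

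**Step 2. The plan's own figure.** The plan gives no expected device AE rate, so there is none to reproduce. The only plan figure used here is the target of 24 in section 16.22. Its base of 18 follows from the normal approximation for one proportion, 1% against 10%, one-sided alpha 0.10, power 80%:

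n = [(1.2816 × √(0.01 × 0.99) + 0.8416 × √(0.10 × 0.90)) / 0.09]² = 17.83, rounded up to 18.

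Adding 10% and 20% gives 18 × 1.30 = 23.4, rounded up to 24.

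**Step 3. Effect on the device rate (illustration).** Let k be the number of implanted patients outside the set. The documents give no value, so k is an assumption, shown from 0 to 3 of 24 implanted. Suppose there are no complications among the remaining 24 − k and one in each of the k. Intervals are Clopper–Pearson. For zero events in n the upper limit is 1 − 0.025^(1/n); for n = 23 it is 1 − 0.025^(1/23) = 14.8%.

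| k | Rate as the plan would report it | Rate in all implanted |
|---|---|---|
| 0 | 0/24 = 0% (0 to 14.2%) | 0/24 = 0% (0 to 14.2%) |
| 1 | 0/23 = 0% (0 to 14.8%) | 1/24 = 4.2% (0.1 to 21.1%) |
| 2 | 0/22 = 0% (0 to 15.4%) | 2/24 = 8.3% (1.0 to 27.0%) |
| 3 | 0/21 = 0% (0 to 16.1%) | 3/24 = 12.5% (2.7 to 32.4%) |

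The rows for k = 2 and 3 are deliberately extreme, because every excluded patient has an event. The row for k = 1 is enough to make the point. If the excluded patient were replaced, so that 24 were treated, the comparison would be 0/24 = 0% against 1/25 = 4.0%, which is the same picture.

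**Step 4. Explant.** Monitoring runs to 12 months after treatment (4.0) and on-study status ends one year after RT (4.1). The last scheduled AE assessment is at 12 months ± 6 weeks. No explant date and no AE window after explant are given. An explant done while on study is covered by the Unscheduled column. For one done at or after study exit, no section says how its AEs reach the device summary.

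**The case against.** The strongest reply is that these complications are not lost. AEs are marked in Table 5.0 before treatment, during it, at each follow-up and at unscheduled visits. Section 11.2 monitors placement events with no limit to treated patients. The device stopping rule in section 16.41 counts the first 10 patients without requiring that they be treated, and the study is reviewed monthly. Sections 11.5 and 13.1 keep some data on ineligible patients. All of this stands. A reader might infer that device complications in untreated patients go unseen; the documents do not support that. What they leave is the reported rate.

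The safeguards do not restore them to that rate. The stopping rule triggers suspension and does not define an estimate. Reporting under section 10.31 requires an unanticipated event, whereas bleeding and infection are already listed as insertion risks. Section 10.11 defines an AE by association with standard-of-care treatment, and the solicited list in 10.23 has no implant-site item.

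Three further inferences are tempting and also fail:

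- That routine explants as a class escape AE observation. No explant date is given, so neither their number nor the share after study exit can be stated.
- That the 10% allowance in section 16.22 measures how many leave the set. It combines loss to follow-up with ineligibility; a treated patient who is later lost stays evaluable under 16.323, and no rate of never starting treatment is given.
- That patients with complications are the very ones excluded. Nothing in the documents says a device complication would keep a patient from RT. Nor are the 120 days a stated interval between implant and RT; they are the general pre-treatment window.

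**Conclusion.** The concern holds as a mismatch between analysis set and exposure. Applied as written, sections 16.2 and 16.323 remove from the device-safety rate any implanted patient who never starts cancer treatment or is found ineligible, even if the complication was recorded.

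The number affected is unknown and may be zero, in which case nothing changes. If it is one patient with one complication among 24 implanted, the report moves from 4.2% (0.1 to 21.1%) to 0% (0 to 14.8%). This rests on 24 implants, with insertion before the patient leaves the study. The intervals overlap widely, so the harm lies in a possible statement of no complications rather than in a precise bias.

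The explant point is secondary: a missing specification, not a demonstrated loss of data. The whole should be corrected because the correction is nearly free, but it does not touch the primary endpoint.

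**What to change.** 1. In sections 16.2 and 16.323, define a device-safety set: every patient in whom ICM insertion was attempted, regardless of eligibility and of whether cancer treatment began. Count device- and procedure-related AEs from insertion. Use this set for the device-safety estimates and their intervals.
2. Keep the existing set of eligible, treated patients for cancer-treatment AEs, and say whether treatment there means RT or any cancer treatment.
3. In section 11.2, widen the scope from placement to cover extraction as well.
4. In section 13.2, state that device-related AEs continue to be collected in implanted patients who receive no RT or receive it elsewhere.
5. State the AE collection window after explant, and how AEs of an explant at or after study exit enter the device-safety summary. Section 4.1 should be consistent with this. The length of the window is for the study team to set.

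The cost is wording in these sections and, where explant follows study exit, some AE follow-up beyond it. The device AE rate may come out slightly less favourable. Sample size and primary analysis are unchanged.
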